### 10.3 Adverse Event Assessment

All subjects who have been exposed to the study treatment will be evaluated for Adverse Events as defined in this protocol. All adverse events, regardless of severity and whether or not they are ascribed to the study treatment, will be recorded in the source documents using standard medical terminology. Pre-existing conditions or diseases present at baseline that remain stable or change in a manner consistent with natural disease progression are not considered Adverse Events.

All Adverse Events will be evaluated beginning at the time of onset, and evaluation will continue until resolution or until the investigator determines that the subject's condition is stable. The investigator will take appropriate and necessary therapeutic measures required for resolution of the Adverse Event. Any medication necessary for the treatment of an Adverse Event must be recorded on the concomitant medication source document.

All AEs will be characterized by the following criteria:

- Event term
- Intensity or severity
- Expectedness
- Relationship to study treatment
- Outcome
- Treatment or action taken.

Whenever possible, recognized medical terms should be used when recording AEs. Colloquialisms and/or abbreviations should not be used. Only one medical concept, preferably a diagnosis instead of individual symptoms, should be recorded as the event.

If known at the time of reporting, a diagnosis (i.e., disease or syndrome) should be recorded on the source document rather than individual signs and symptoms (e.g., record congestive heart failure rather than dyspnea, rales, and cyanosis). If a constellation of signs and/or symptoms cannot be characterized with a single medical diagnosis or syndrome and they are considered unrelated to an encountered syndrome or disease at the time of reporting, these individual events should be recorded as separate AEs (e.g., if congestive heart failure and severe headache are observed at the same time, each event should each be recorded as an individual AE). If a diagnosis was not initially reported, and is subsequently established it should be reported as follow-up information and the original AE documents updated accordingly.

Adverse Events occurring secondary to other events (e.g., sequelae) should be identified by the primary cause; a "primary" event, if clearly identifiable, should represent the most accurate clinical term to record as the AE event term. For example:

*Orthostatic hypotension ⇒ fainting and fall to floor ⇒ head trauma ⇒ neck pain*

The primary event is orthostatic hypotension and the sequelae are head trauma and neck pain.

#### 10.4 Classification of Adverse Events by Intensity / Severity

All Adverse Events should be graded on a four-point scale (mild, moderate, marked, severe) for intensity/severity. These definitions are as follows:

**Mild:** Transient discomfort; no medical intervention/therapy required and does not interfere with daily activities.

**Moderate:** Low level of discomfort or concern with mild to moderate limitation in daily activities; some assistance may be needed; minimal or no medical intervention/therapy required.

**Marked:** Considerable discomfort with limitation in daily activities, some assistance usually required; medical intervention/therapy usually required.

**Severe:** Extreme discomfort and limitation in daily activities, significant assistance required; **significant** medical intervention/therapy required.

There is a distinction between the severity and the seriousness of an Adverse Event. Severity is a measurement of intensity; thus a severe reaction is not necessarily a Serious Adverse Event. For example, a headache may be severe in intensity, but would not be serious unless it met one of the criteria for Serious Adverse Events.

#### 10.5 Classification of Adverse Events by Expectedness / Relatedness

All AEs will be evaluated as to whether they are expected or unexpected, as defined below:

**Expected (anticipated):** An Adverse Event is expected when the nature, severity, or degree of incidence was previously described.

**Unexpected (unanticipated):** An Adverse Event is unexpected when the nature, severity, or degree of incidence was not previously described.

All AEs will be evaluated as to whether they are related to the device, as defined below:

**Not Related:** Strong evidence exists that the Adverse Event definitely has a cause other than the investigational device (e.g. pre-existing condition or underlying disease, concurrent illness, or concomitant medication), or the investigational device cannot be implicated based on the available information

**Possibly Related:** There is a temporal association with the investigational device and it cannot be excluded as a cause but other etiologies are also likely to be the cause based upon available information

**Probably Related:** There is a temporal association with the investigational device which makes a causal relationship probable where other etiologies are possible but unlikely to be the cause, based upon available information.

**Definitely Related:** Strong evidence exists that the investigational device definitely caused the Adverse Event. There is a temporal relationship between the event onset and the investigational device and the subject's clinical state and concomitant therapies have

been ruled out as a cause, based upon available information.

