A total of 645 eyes of 330 subjects were enrolled and implanted with the PSI [REDACTED] in this clinical study. Subjects implanted with the PSI [REDACTED] experienced clinically meaningful improvement with DCNVA (Sloan) at 40cm. DCNVA (Sloan) of 20/40 or better was achieved by 80% (237/298) of subjects at 12 months, by 84% (210/249) of subjects at 18 months and by 91% (120/132) of subjects at 24 months.

Further, during the course of this clinical trial no persistent loss in BCDVA or BCNVA was observed in any eye. BCDVA remained generally unchanged from baseline through the 24 month visit and all (100%) of the PSI treated eyes achieved BCNVA of 20/32 or better at all postoperative examinations.

The PSI [REDACTED] has not been modified since its introduction into the clinical trial conducted under G970152, and there are no plans to modify this model of the PSI.

Frequently reported ocular adverse events in this clinical trial were dry eye and improper conjunctival closure after the surgical procedure, the latter resulting in exposed implant segments. Exposed segments were treated with revised conjunctival closures. Other ocular adverse events included conjunctival tags, corneal abrasions, conjunctival injection, superficial punctate keratitis (SPK), conjunctival thinning, and exposed suture. All of these were transient in nature and resolved without sequelae, generally with no or limited medical intervention. IOP increases secondary to postoperative administration of topical steroid drops were reported; in all cases, IOP returned to the baseline level after discontinuation of the steroid drops and/or short-term use of IOP lowering medications in a few cases.

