### **Other**

- Eye pain requiring oral prescription pain medication after 1 week postoperative
- Allergic reactions to medications, devices, sutures or anesthesia
- Other findings worsening two grades from baseline to a grade of +3 or +4

\* Refer to [Appendix 6: Anterior Segment Ischemia \(ASI\): Detection, Mitigation and Reporting](#)

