### **4.2 Scheduled Meetings**

Meetings will be held by phone or in person twice per year during the Clinical Trial. The frequency of scheduled meetings may change at the discretion of the DSMB Chairperson depending on subject enrollment and safety event rates. Meetings will also be held upon the occurrence of a device-related SAE or UADE, or at the request of the Medical Monitor.

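### Relatedness is graded against the device only, so a serious harm from the procedure or its drugs can be graded unrelated and miss prompt DSMB review

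*Combined protocol and SAP*

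**What the plan says.** Section 10.3 lists the attributes to be recorded for every adverse event, among them "Relationship to study treatment". Section 10.5, which should supply the scale for that attribute, says instead: "All AEs will be evaluated as to whether they are related to the device, as defined below". Its four grades run from Not Related to Definitely Related, and all refer to the investigational device.

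Not Related has two limbs. The first is strict: "Strong evidence exists that the Adverse Event definitely has a cause other than the investigational device", with the examples "pre-existing condition or underlying disease, concurrent illness, or concomitant medication". The second is looser and applies when the device cannot be implicated on what is known.

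The DSMB charter (Appendix 5, section 4.2) provides for two scheduled meetings a year and adds: "Meetings will also be held upon the occurrence of a device-related SAE or UADE, or at the request of the Medical Monitor". Section 5.1 of the charter uses the same device-related wording for notifying the chair.

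The protocol expects harms that do not come from the implant itself. Section 6.3 says of the earlier trial that "IOP increases secondary to postoperative administration of topical steroid drops were reported". Section 10.8 lists, under Other, "Allergic reactions to medications, devices, sutures or anesthesia", and lists scleral perforation among intraoperative events.

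**The concern.** The treatment under test is more than an implant. Section 11.0 describes the study as an evaluation of the scleral implant procedure. That procedure involves tunnel creation, conjunctival sutures, anesthesia and the perioperative drugs set out in Section 8.4. A scale that asks only about the device has no place for harm from these other components.

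Two things are at stake. The first is consistent attribution. Only the 60-subject sub-study has a concurrent control group, and only for 6 months, so for most subjects the investigator's judgment is the main means of separating implant, surgical and drug harms. The second is oversight. The DSMB's event-driven route depends on the relatedness grade, so a gap in the scale becomes a gap in what the board hears promptly.

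**Working it through.** No figure in the plan bears on this, so the check sets the sections against each other and follows example events through them.

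**Step 1: the target of attribution.** Section 10.3 asks about study treatment; 10.5 asks about the device. No visible section gives a scale for the procedure or the drugs. Section 4.2 of the protocol describes the VisAbility Implant System as integrated surgical instrumentation, but 10.5 does not say whether its device is that System or the implant alone.

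**Step 2: which grades are open for harms the protocol anticipates.**

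| Event | Grade available under 10.5 |
|---|---|
| IOP rise that the investigator firmly attributes to the directed topical steroid | Not Related by the first limb, if the steroid counts as concomitant medication (the text does not say) |
| The same rise, with the device not excluded | Possibly Related |
| Allergic reaction to anesthesia or a postoperative drug | Not Related by either limb, if the device is judged not to be implicated |
| Scleral perforation, device read as the System | Can be graded related |
| Scleral perforation, device read as the implant only | Can be Not Related, by the second limb |
| Harm in an eye prepared for surgery but never implanted (in the Safety Cohort under 11.4), device read as the implant only | Nothing for the event to be related to, so Not Related |

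The second limb reads in full context: "concurrent illness, or concomitant medication), or the investigational device cannot be implicated based on the available information". Two sites could grade the same event differently and both comply with the text.

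**Step 3: what the grade controls.** Suppose the event is serious and graded Not Related.

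1. The sponsor still hears within 24 hours, because 10.1 covers any SAE.
2. The device-related limb of Appendix 5, sections 4.2 and 5.1, is not met.
3. The UADE limb needs an association with the device and an effect not previously identified in nature, severity or incidence (10.2). An event already listed in 10.8 would ordinarily fail this unless its severity or frequency was new.
4. A meeting then follows only if the Medical Monitor asks for one.
5. Otherwise the DSMB sees the event at the next scheduled meeting. With two meetings a year, evenly spaced (my assumption), the longest wait is 12 / 2 = 6 months.

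The charter also does not say which 10.5 grades count as device-related. It is therefore unclear whether even a Possibly Related SAE triggers notice.

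**Step 4: what the grade does not control.** All events are recorded whatever their attribution (10.3). Section 7.4 plans AE rates and 11.9 plans safety summaries, neither filtered by relatedness. IOP change is tabulated by size at each visit for all implanted eyes. The safety sample size in 11.3 concerns any event with a true probability of 1%.

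**The case against.** The strongest reply is that the scale is harder to misuse than it looks. The first limb of Not Related demands strong evidence of a definite other cause, and Possibly Related takes events close in time to implantation where the device cannot be excluded. Surgery, anesthesia and sutures are not among the named examples of other causes. If the device means the System, harms from tunnel creation are already covered. A definition may also sit in blacked-out text. Section 8.4 presents its drugs as guidelines, several of them optional. All of this stands, and it limits the point to what can happen under the text.

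The oversight reply is also partly right. The Medical Monitor can call a meeting, the chair can change the meeting frequency in light of safety event rates, and the scheduled reports contain AE listings not limited to related events. These reduce the gap but do not close it, because none obliges anyone to tell the DSMB promptly about a serious anticipated harm graded Not Related.

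Three stronger readings are tempting, and the documents support none of them:

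- A reader might infer that every steroid, anesthetic or allergy event will be graded Not Related. Step 2 shows that the grade depends on the investigator's certainty and on how the device is read.
- A reader might infer that the planned AE rate will be too low. No visible planned output uses a treatment-related rate.
- A reader might want a count of misgraded events. The documents give no rate for such events, and an assumed one would not address the DSMB question, since a non-serious event triggers no unscheduled meeting even when it is device-related.

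**Conclusion.** The point holds in limited form. Sections 10.3 and 10.5 name different targets for attribution. The device is undefined in the visible text of 10.5, and harms from the procedure or its drugs can be graded Not Related. The practical consequence is confined to serious, already anticipated harms that receive that grade and for which the Medical Monitor does not request a meeting. For these, DSMB review may wait up to about six months, on the assumption of evenly spaced meetings. Any attribution summary that is produced would also be harder to interpret.

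Event capture, SAE notice to the sponsor, the planned overall AE rates and both primary effectiveness objectives are unaffected. The change is worth making because it improves safety oversight at low cost, but no planned analysis depends on it. If a redacted section defines the device as the full System, the gap narrows to anesthesia, sutures, drugs and any part of the surgery outside the System.

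**What to change.** 1. In 10.3 and 10.5, use one target for attribution, and state whether the device is the implant or the System.
2. In 10.5, grade relatedness separately to (a) the implant or System, (b) the surgical procedure, including anesthesia and sutures, and (c) protocol-directed perioperative medications. Say that the drugs under (c) are not a ground for calling an event unrelated to study treatment.
3. Define an event as related to study treatment when it is at least possibly related to any of the three.
4. In Appendix 5, sections 4.2 and 5.1, tie the unscheduled meeting and the notice to the chair to SAEs meeting that definition, plus UADEs. Keep the Medical Monitor's right to request a meeting.

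The cost is two extra eCRF fields and short edits to 10.3, 10.5 and Appendix 5. Reported counts of related events will be slightly higher and the DSMB will receive a few more notices. No visit, treatment or primary analysis changes.

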### **10.6 Adverse Event Outcome**

The clinical outcome of an Adverse Event will be recorded and characterized as follows:

- Resolved without sequelae
- Resolved with sequelae (specify)
- Ongoing (i.e. continuing at time of study discontinuation)
- Death.

### **10.7 Treatment or Action Taken**

The clinical treatment of an Adverse Event will be documented and characterized as follows:

- None
- Medical Intervention
- Surgical Intervention
- Other

### **10.8 Anticipated Adverse Events**

Adverse Events that might reasonably be expected to occur in this study are listed below. The time periods refer to the exam visit that occurs corresponding to the post-operative follow-up visit schedule (i.e., 3 months means the 3 month postoperative visit). Exams for the primary eye and fellow eye may be done at the same visit if windows permit. For purpose of determining whether a fellow eye event is an Adverse Event, the time period used shall be based on the date of the fellow eye surgery.

These specific examples of anticipated Adverse Events include, but are not limited to:

#### **Intraoperative Events**

- Scleral perforation
- Scleral perforation with vitreous prolapse

#### **Lids and Lashes**

- Ptosis
- Onset of or worsening to severe clinically significant lid margin disease (e.g., blepharoconjunctivitis, blepharitis, meibomitis, meibomian gland dysfunction, etc.) after 3 months postoperative

#### **Cornea**

- Corneal dellen after 1 week postoperative
- Corneal abrasion > 2mm after 1 week postoperative
- Dry eye signs (moderate or severe) of corneal and/or conjunctival staining, etc., requiring prescription medication after 6 months postoperative
- Corneal edema (moderate or severe) after 1 month postoperative
- Corneal infiltrate or ulcer

### **Conjunctiva/Sclera**

- Conjunctival cyst
- Conjunctival thinning or erosion
- Moderate or severe conjunctival injection at 3 months postoperative or later
- Subconjunctival hemorrhage after 3 months postoperative

### **Anterior Segment, Iris, Lens**

- Pupil abnormalities persisting after 3 months
- Grade 4 anterior segment ischemia (corneal edema, anterior chamber reaction, and decreased pupil reactivity)\*
- Anterior chamber cells or flare greater than mild at Day 1 through 1 Week
- Anterior chamber cells or flare after 1 week postoperative
- Intraocular Inflammation other than anterior chamber cells and flare (e.g., vitritis)
- Two grade change in lens opacity compared to baseline on two consecutive post-operative visits
- Displaced or missing implant segments

### **Intraocular Pressure**

- Hypotony (IOP < 6mmHg)
- Increase in IOP of > 10mm Hg over baseline or IOP > 30mm Hg at two consecutive visits at 1 week or later

### **BCDVA Loss**

- Decrease in BCDVA of greater than or equal to 2 lines ( $\geq 10$  letters ETDRS) at 3 months or later

### **Fundus**

- Choroidal effusion
- Retinal detachment
- Retinal or vitreous hemorrhage

### **Secondary Surgical Intervention**

- Implant segment removal
- Exposed implant segments or conjunctival retraction requiring conjunctival re-approximation

### **Other**

- Eye pain requiring oral prescription pain medication after 1 week postoperative
- Allergic reactions to medications, devices, sutures or anesthesia
- Other findings worsening two grades from baseline to a grade of +3 or +4

\* Refer to [Appendix 6: Anterior Segment Ischemia \(ASI\): Detection, Mitigation and Reporting](#)

## 11.0 STATISTICAL METHODS

This is a prospective, multicenter study with a randomized, controlled sub-study that is designed to evaluate the safety and effectiveness of the scleral implant procedure. The percentage of primary eyes achieving the effectiveness endpoint will be evaluated at 12 months postoperatively. Within the study cohort, a subgroup will be randomized on a 1:1 ratio to a surgery group and a control group. Subjects in the randomized control group will not receive surgery and will be examined at 3 months and 6 months. After completion of the 6 month observation period, subjects in the randomized control group will be eligible to receive surgery as part of the 360 subject cohort. This randomized controlled sub-study will be used to evaluate the effectiveness of the scleral implant procedure in the randomized surgery group compared to effectiveness in the randomized control group at 6 months postoperatively.

The effectiveness endpoint, hypotheses, sample size calculations, analysis population, handling of missing data, analysis methods, and analysis of safety data are as follows.

### 11.1 Effectiveness Endpoint

The effectiveness endpoint is:

Achievement of distance corrected near visual acuity (DCNVA) of Snellen equivalent 20/40 or better (at 40 cm) and at least 10 letters (ETDRS) improvement in DCNVA in the primary eye.

### 11.2 Statistical Hypotheses

For the effectiveness endpoint, two objectives must be met.

#### Objective #1:

The scleral implant procedure is defined as successful if 75% or more of primary eyes achieve the effectiveness endpoint at 12 months postoperative. The corresponding statistical hypothesis is as follows:

$H_0$  (null hypothesis):  $p < 0.75$

$H_a$  (alternative hypothesis):  $p \geq 0.75$

Where,  $p$  is the probability that subjects achieve the effectiveness endpoint at 12 months postoperative (12-month responder rate).

#### Objective #2:

An analysis of the randomized surgery group and randomized control group will be conducted. The randomized surgery group is defined as successful if the percentage of primary eyes achieving the effectiveness endpoint at 6 months postoperative (6-month responder rate) is higher than the percentage in the randomized control group. The corresponding null and alternative hypotheses are as follows:

$H_0$  (null hypothesis):  $p_1 \leq p_2$

$H_a$  (alternative hypothesis):  $p_1 > p_2$

Where:

- $p_1$  is the percentage of primary eyes in the randomized surgery group who achieve the effectiveness endpoint at 6 months.
- $p_2$  is the percentage of primary eyes in the randomized control group who achieve the effectiveness endpoint at 6 months.

The primary eye is defined as the subject's dominant eye and the eye that will undergo surgery first. It is intended that all subjects will also undergo surgery in the fellow eye at a subsequent date as specified in the protocol.

### 11.3 Sample Sizes

Both Objective #1 and #2 will need to be statistically significant in order to determine the effectiveness of the study device. Therefore the two-sided significance level of 0.05 is not adjusted for the multiplicity.

#### Full Study Cohort Effectiveness Endpoint

The sample size calculation for the statistical hypotheses described for Objective #1 in Section 11.2 is based on the following criteria:

- The two-sided significance level = 0.05 (or one-sided significance level = 0.025).
- The statistical power = 90% at  $p = 0.825$ . The assumption of true responder rate of 0.825 is based on the simple average of success rate observed in previous Refocus clinical study data, as follows:
  - Disposable Scleratome group had an observed success rate of 88%.
  - Re-usable Scleratome group had an observed success rate of 77%.
  - Simple average of 88% and 77% is 82.5%.
- Binomial distribution is used for sample size calculation.

Based on the criteria above for Objective #1, 330 treated primary eyes should be available for analysis at 12 months. If a dropout rate of 10% of subjects by 12 months is considered, then the surgery cohort should include approximately 360 treated primary eyes.

For safety analysis, in order to detect an Adverse Event (AE) with a true probability of occurrence among subjects of 1% with 95% probability, based on the binomial distribution, a sample of at least 299 eyes would be required (in accordance with ANSI Z80 29 18Nov2013 AIOL [rev20]). Assuming a drop-out rate of approximately 10% of subjects by 12 months, the surgery cohort should include a minimum of 333 treated primary eyes.

A sample size of 333 treated primary eyes will meet the sample size requirements for both safety and effectiveness. The study cohort is planned for 360 surgery subjects at up to 14 study sites. However, no site may enroll and determine to be eligible more than 20% of the subject surgery cohort.

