### **3.0 STUDY SYNOPSIS**

The objective of this study is to evaluate the safety and effectiveness of the VisAbility Implant System (VIS) for the improvement of near visual acuity in presbyopic patients. This is a prospective clinical study that will enroll and determine eligible a total of 360 subjects ranging in age between 45 and 60 years of age at up to 14 clinical sites. Subjects will be implanted with the VisAbility Implant [REDACTED] in the primary eye and then in the fellow eye no sooner than 14 days later. Subjects will be examined at one day, one week and at 1, 2, 3, 6, 12, 18 and 24 months post-operatively.

The study will also include a 60 subject randomized controlled sub-study at 3 investigational sites. Subjects enrolled and eligible at these sites will be randomized (1:1 ratio) to a surgery group or a control group. Subjects randomized to the surgery group will undergo surgery and will be followed for 24 months in the same manner as the larger non-randomized surgical group. Subjects randomized to the control group will be followed for 6 months, and will be eligible to undergo surgery after completion of this 6-month follow-up period.

The primary endpoint is achievement of distance corrected near visual acuity (DCNVA) of Snellen equivalent 20/40 or better (at 40 cm) and at least 10 letters (ETDRS) improvement in DCNVA in the primary eye.

This endpoint will be evaluated against two objectives, a) 75% or more of primary eyes achieve the effectiveness endpoint at 12 months postoperative and b) the percentage of primary eyes achieving the effectiveness endpoint at 6 months postoperative (6-month responder rate) is higher than the percentage in the randomized control group.

A PMA application will be submitted when the full study cohort has completed the 12 month follow-up visit.

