The study also includes a 60 subject randomized controlled sub-study at 3 investigational sites. Eligible subjects enrolled at these sites will be randomized (1:1 ratio) to a surgery group or a control group. Subjects assigned to the randomized surgery group will be implanted and followed for 24 months in the same manner as the larger non-randomized surgery group. Subjects randomized to the control group will be followed for 6 months, and will be eligible to undergo VisAbility Implant surgery after completion of the six month observation period. These subjects that elect surgery will be followed for 24 months in accordance with the same schedule as the non-randomized surgery group. Randomized control group subjects who do not chose to undergo VisAbility Implant surgery at the end of the 6 month observation period will be exited from the study at that time.

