## **8.8 Subject Termination or Withdrawal**

Subjects may be terminated from the study if the Investigator believes that continued participation in the study may jeopardize the subject's health or welfare. Subjects may also elect to withdraw from the study at their discretion. Every effort will be made to encourage the subject to maintain compliance with the protocol and to continue in the study. Further, every effort will be made in both instances to conduct examinations as determined by the Investigator to ensure the safety of the subject. The Sponsor should be notified promptly by the Investigator upon the termination or withdrawal of a subject by completion of the Study Exit form. Terminated or withdrawn subjects may not be replaced with additional enrolled and eligible subjects. Subjects who have all implant segments removed (explanted) from both eyes will be exited from the study after at least 3 months post-explant follow-up.

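### The figure 360 means eligible subjects (30 controls included) in some sections and operated eyes in Section 11.3; evaluable eyes come to about 297 to 324, not 330, with power about 87% to 90%

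*Combined protocol and SAP*

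**What the plan says.** Section 11.3 (Full Study Cohort Effectiveness Endpoint) sizes Objective #1 with the exact binomial distribution. The significance level is given as "The two-sided significance level = 0.05 (or one-sided significance level = 0.025"). The power line reads "The statistical power = 90% at" a true responder rate of 0.825. The section asks for 330 treated primary eyes available at 12 months and, allowing 10% dropout, states that "then the surgery cohort should include approximately 360 treated primary eyes". It closes with "The study cohort is planned for 360 surgery subjects at up to 14 study sites". In between, it derives a minimum of 333 treated eyes from the safety requirement of 299.

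Elsewhere 360 is a different count. The synopsis says that the study "will enroll and determine eligible a total of 360 subjects", and Sections 7.2 and 7.5 say the same in substance. Section 11.0 describes the randomized subgroup as lying within the study cohort and says that after six months "subjects in the randomized control group will be eligible to receive surgery as part of the 360 subject cohort". The sub-study part of Section 11.3 fixes the controls at 30.

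Three further provisions bear on how many eyes are operated:
- Surgery for controls is elective. Under Section 7.2, control "subjects who do not chose to undergo VisAbility Implant surgery at the end of the 6 month observation period will be exited", and under Section 8.5.2 the six-month visit serves as the eligibility examination for those who elect it.
- Section 11.5 has a category for eligible subjects who never reach surgical preparation. No number is given.
- Section 8.8 states: "Terminated or withdrawn subjects may not be replaced with additional enrolled and eligible subjects".

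Section 11.6 limits the Objective #1 analysis to observed 12-month data from operated primary eyes, with explanted eyes counted as failures.

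**The concern.** A control who declines surgery is one of the 360 eligible subjects but contributes no eye to Objective #1. The eligible count and the operated count can therefore differ by up to 30 before any surgical withdrawals. Section 11.3 uses the larger figure as though it were the operated count.

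Objective #1 must succeed for the study to succeed (Sections 11.3 and 11.8), so its stated size and power should be figures that the enrolment rule can produce. As written, a reader cannot tell whether enrolment closes at 360 eligible or 360 operated subjects. Section 7.2 applies the 20% site cap to the eligible cohort, while Section 11.3 applies it to the surgery cohort, so the ambiguity also reaches an operational rule.

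**Working it through.** **Inputs.** From Section 11.3: performance goal 0.75, assumed rate 0.825, one-sided level 0.025, 330 evaluable eyes, 10% dropout, 30 controls. From Section 11.8: success requires an exact one-sided 97.5% lower limit of at least 75%. Not in the documents: how many controls elect surgery (taken as 0 to 30) and how many eligible subjects never reach surgery (taken as 0 in the table).

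**Method.** For n evaluable eyes, the critical count r is the smallest value with P(X ≥ r | n, 0.75) ≤ 0.025. This is equivalent to a Clopper-Pearson lower limit of at least 0.75. Power is P(X ≥ r | n, 0.825).

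**The plan's own figure.** At n = 330, r = 264, the attained level is 0.0192 and power is 89.6%. The one-sample normal formula with continuity correction gives 330.3. The 330 is reproduced.

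**Inflation for dropout.** 330 / 0.90 = 366.7, so 367 treated eyes are needed to expect 330 evaluable. With 360 treated, 360 × 0.90 = 324. Going from 360 to 330 is a loss of 30/360 = 8.3%, not 10%. This shortfall has nothing to do with the controls.

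**Counting the controls.** If 360 are eligible and 30 of them are controls, 360 − 30 = 330 are assigned to immediate surgery. Operated eyes are then 330 plus the number of controls who elect surgery.

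| Controls operated | Treated eyes | Evaluable at 10% dropout | r | Exact power at that n | Power averaged over random dropout |
|---|---|---|---|---|---|
| 0 of 30 | 330 | 297 | 238 | 87.4% | 87.0% |
| 15 of 30 | 345 | about 310 | 248 | 89.0% | 88.4% |
| 30 of 30 | 360 | 324 | 259 | 89.9% | 89.9% |

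The last column lets the number of evaluable eyes vary as binomial with retention 0.90. It is the fairer summary because exact power is saw-toothed in n: between 297 and 324 it runs from 86.2% (n = 299) to 90.8% (n = 322).

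**Against the plan's own minimum.** With no crossover, 330 treated eyes fall short of the stated 333. At least three controls must be operated, with no surgical withdrawals, to reach it. The 297 evaluable eyes are also just under the 299 used for the 1% adverse-event criterion, but the effect is trivial: 1 − 0.99^297 = 94.9%, against the 95% sought.

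**The case against.** The strongest reply is that Section 11.3 itself says the cohort is planned for 360 surgery subjects. The Section 11.0 sentence on controls can also be read as making 360 the surgical cohort, which controls join only when operated. That stands: a reader might infer that 360 is definitely a count of eligible subjects, but the documents contradict each other and do not settle it.

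A reader might also infer that the 90% power is simply not delivered. The figures do not support this. At 324 evaluable eyes exact power is 89.9%, no lower than the 89.6% at the plan's own 330, and at half crossover it is 89.0%. Only the low-crossover end loses an appreciable amount, and no crossover rate is given.

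Nor can the whole range of 297 to 324 be blamed on the controls. The 324 end arises with every control operated, because 367 was rounded down to about 360. The fact that 360 treated eyes have only a 17% chance of yielding 330 or more evaluable does not show lost power either: with 367 treated the chance is still only 56%, and power averaged over dropout at 360 treated is 89.9%.

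On surgical withdrawals, the documents do not say whether the no-replacement rule in Section 8.8 covers eligible subjects who never reach surgery, or whether the 10% dropout already includes them. So 330 treated and 297 evaluable are not firm floors, and no lower figure can be derived.

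The decision rule, the analysis set and the type I error are unaffected. Explanted eyes stay in the analysis as failures, so they do not reduce n.

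**Conclusion.** Wrong as written, with a modest consequence. The documents use 360 in two incompatible ways, and at the stated 10% dropout neither gives an expected 330 evaluable eyes.

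- If 360 are operated, about 324 are evaluable. The stated size is missed, but power remains about 90%.
- If 360 are eligible, between 330 and 360 are operated, or fewer with surgical withdrawals. About 297 to 324 are evaluable, and power averaged over dropout is about 87% to 90%. At the low end the treated count is also below the plan's own minimum of 333.

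The lower figures assume a true rate of 0.825, dropout of exactly the planned 10%, and no crossover. The size error is firm. The power loss, from nothing to about 3 points below the nominal 90%, depends on a crossover rate that the documents do not state.

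**What to change.** Choose one definition of 360 and use it in Sections 3.0, 7.2, 7.5, 11.0 and 11.3, including the base of the 20% site cap.

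- **If 360 means eligible subjects:** remove the statement that 360 surgery subjects are planned, and restate Section 11.3 along these lines: *up to 360 treated primary eyes (330 if no control elects surgery, fewer with surgical withdrawals); about 297 to 324 evaluable at 12 months with 10% dropout; power at p = 0.825, averaged over dropout, about 87% to 90% depending on control crossover.*
- **If 360 means operated subjects:** say so in Sections 3.0, 7.2 and 7.5, and restate the evaluable number as 324 with about 90% power.

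Under either choice, check the sentence saying that 333 treated eyes suffice for effectiveness against the restated figures, since 333 × 0.90 = 299.7, not 330.

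The cost is protocol and SAP wording, and a slightly less favourable stated size and power. No added enrolment is needed.
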